5.3 Risks/Benefits

Urethral stricture disease can be difficult and expensive problem for urologists to manage. As observed with this patient population, conservative management involves frequent straight catheterization or management with an indwelling foley catheter that can decrease the patient's quality of life and increase the patient's risk of urinary tract infections. Other minimally invasive treatments have shown limited efficacy or have increased morbidity. Surgical options that are effective, however, involves higher risks, require extensive anesthesia and are often poor options for elderly patients, patients with significant comorbidities, or patient who simply do not wish to undergo such extensive surgery. Therefore, treatments with injections may provide sufficient potential benefit and an acceptable potential for risk for this study population.

5.4 Dosage and Administration

On day of treatment, prior to study drug administration, photographic evidence captured with urethral ultrasound will be used to confirm eligibility criterion: < Grade 5 spongiosis. If the patient's urethral ultrasound for Baseline/Screening was performed more than 30 days prior to the treatment day (Day 0), it will be performed again on the treatment day (Day 0) prior to study drug administration to re-confirm the patient's study eligibility and to allow for proper procedural planning for study treatment.

On day of treatment, patients will undergo instillation of local anesthesia (20 mL of 2% urethral lidocaine jelly), the patient will undergo cystoscopy, transurethral injection (via a 70 cm 4.8 Fr flexible cystoscopic needle with a 23 gauge needle tip manufactured by Laborie®, Ontario, Canada) of 0.08ml of XIAFLEX® (0.58 mg of XIAFLEX® mixed with 0.39 mL of sterile diluent) in a single location within the stricture, chased by an additional 0.25 mL of reconstituted XIAFLEX® to allow for clearance of the original 0.08 mL of reconstituted XIAFLEX® from the transurethral syringe into the urethral stricture. This is based on 0.25 mL residual fluid that remains within the lumen of the injeTAK syringe. Thus, by adding the additional 0.25 mL of XIAFLEX® as a chase, we are expecting the original total of 0.08 mL of XIAFLEX® to be injected into the area of scarring. The depth and location of the needle will be determined procedurally with urethral ultrasonography with the needle in a semi-parallel manner into the plaque as to avoid perforation into nearby structures. Injections will be performed at a single site identified on ultrasound as appropriate, and avoiding the 6 o'clock and 12 o'clock sites where potential perforation can lead to additional complications. The site of injection will be recorded accordingly for safety monitoring following treatment. The remaining 0.25 mL that remains in the injection syringe will be discarded per institutional policy for biohazard disposal.

Reconstitution of the Lyophilized Powder for Peyronie's Disease (taken from XIAFLEX® package insert)

1. Before use, remove the vial containing the lyophilized powder of XIAFLEX® and the vial containing the diluent for reconstitution from the refrigerator and allow the two vials to stand at room temperature for at least 15 minutes and no longer than 60 minutes. Visually inspect the vial containing XIAFLEX®. The cake of lyophilized powder should be intact and white in color.
2. After removal of the flip-off cap from each vial, using aseptic technique swab the rubber stopper and surrounding surface of the vial containing XIAFLEX® and the vial containing the diluent for reconstitution with sterile alcohol (no other antiseptics should be used).

3. Use on the supplied diluent for reconstitution. The diluent contains calcium which is required for the activity of XIAFLEX®.
4. Using a 1 mL syringe with 0.01 mL graduations with a 27-gauge ½-inch needle, withdraw a volume of 0.39 mL of the diluent supplied.
5. Inject the diluent slowly into the sides of the vial containing the lyophilized powder of XIAFLEX®. Do not invert the vial or shake the solution. Slowly swirl the solution to ensure that all of the lyophilized powder has gone into solution.
6. The reconstituted XIAFLEX® solution can be kept at room temperature (20° to 25°C/68° to 77°F) for up to one hour or refrigerated at 2° to 8°C (36° to 46°F) for up to 4 hours prior to administration. If the reconstituted XIAFLEX® solution is refrigerated, allow this solution to return to room temperature for approximately 15 minutes before use.
7. Discard the syringe and needle used for reconstitution and the diluent vial.

5.5 Formulation

XIAFLEX® will be supplied in single-use glass vials containing 0.9 mg of collagenase clostridium histolyticum as a sterile, lyophilized powder for reconstitution. Sterile diluent for reconstitution will be provided in a package in a single-use glass vial containing 3 mL of 0.3 mg/mL calcium chloride dehydrate in 0.9% sodium chloride.

5.6 Packaging and Labeling

Study drugs packaging and labeling will be provided as marketed. No modifications to the packaging and labeling will be made. A single-use package will consist of one carton containing a single-use vial for XIAFLEX® and a single-use vial of sterile diluent.

5.7 Storage and Handling

Prior to reconstitution, the vials of XIAFLEX® and diluent should be stored in a refrigerator at 2°C to 8°C (36° to 46°F). The reconstituted XIAFLEX® solution can be kept at room temperature (20° to 25°C/68° to 77°F) for up to one hour or refrigerated at 2° to 8°C (36° to 46°F) for up to 4 hours prior to administration. The Clinical Research Center's personnel at USF Health South Tampa Center for Advanced Healthcare will be monitoring study drug storage integrity (i.e. refrigerator temperature monitoring). Records and notifications of temperature excursions will be provided to the Principal Investigator and study coordinator accordingly. The Principal Investigator and study coordinator will ensure the integrity and monitoring of the drug prior to use. The time of each step in the process (i.e. removal from refrigerator, reconstitution, re-refrigeration and/or administration) will be recorded accordingly. Study drug will not be used if the integrity of study drug is compromised.

5.8 Drug Accountability

The Principal Investigator and study coordinator will maintain records of product's delivery and receipt from Endo Pharmaceuticals, Inc. to the drug storage site (USF Health South Tampa Center for Advanced Healthcare, Clinical Research Center at [name] – only accessible to Clinical Research Center's personnel), the inventory at the site, the use by each patient, and disposal of unused products. These records will include dates, quantities, log/batch/serial numbers, expiration or use-by dates, and unique code numbers assigned to the study drugs and study patients.

At each treatment visit, the drugs will be obtained by the study coordinator and will be transported to USF Health South Tampa Center for Advance Healthcare (storage and clinic are in same area), where the treatment will occur.

5.9 Concomitant and Prohibited Medications

XIAFLEX® should be used with caution in patients receiving concomitant anticoagulants (except for low-dose aspirin). For this study, patients with bleeding disorder or anticoagulant use (up to 150 mg/day) other than aspirin are excluded.

5.10 Injection Device

The injection device will be the 70 cm 4.8 Fr flexible injeTAK® cystoscopic needle with a 23 Gauge needle tip manufactured by Laborie®, Ontario, Canada. The 4.8 Fr allows for use with smaller working channels. The black indicator tip provides visual proximity to tissue for accurate placement, safe penetration and gauged puncture depth. The angle and 3-bevel tip is engineered to minimize puncture force. The cannula design also provides easy injection and flexibility while maintaining structural integrity. The needle tip can be adjusted to 0, 2, 3, 4, and 5 mm to accommodate thickness. For this study, the depth of the needle will be set based on pre-operative urethral ultrasound to determine needle location and depth. The needle will be injected in a semi-parallel manner into the plaque as to avoid perforation into nearby structures.

6.0 Methods

6.1 Subject Identification

Potential subjects will be identified through physician referrals (internal/external physicians will only share availability of trial, same information as that already shared with the public on clinicaltrials.gov, to their patients and provide USF urology clinic or research member's contact information for further evaluation – all study recruitment will still occur at the USF urology clinic) and USF urology clinic at the USF Health South Tampa Center for Advanced Healthcare.

6.2 Limited Waiver of Consent

Potential subjects will be identified through physician referrals (internal/external physicians will only share availability of trial, same information as that already shared with the public on clinicaltrials.gov, to their patients and provide USF urology clinic or research member's contact information for further evaluation – all study recruitment will still occur at the USF urology clinic) and USF urology clinic at the USF Health South Tampa Center for Advanced Healthcare – the PI's and sub-investigator's clinic. If the patient has urethral stricture, the PI/sub-investigator will consider the patient for recruitment for the study. The PI/sub-investigator will discuss the study with the patient first, then the research coordinator will be introduced to the patient to complete the informed consent process. During the initial conversation between the investigator/research staff and the patient, the patient may be asked to provide certain health information that is necessary to the recruitment and enrollment process. The investigator/research staff may also review portions of their medical records in order to further assess eligibility prior to study consent – the investigators have a treatment relationship with the potential subjects and the study coordinators do not. They will use the information provided by

the patient and/or medical record (USF EPIC electronic medical record system) to confirm that the patient is eligible and to approach the patient regarding study enrollment. Record review for screening purposes will be completed prior to receiving signed consent. If the patient turns out to be ineligible for the research study, the research staff will destroy all information collected on the patient during the initial conversation and medical records review, except for any information that must be maintained for screening log purposes.

In most cases, the initial contact with the prospective subject will be conducted either by the treatment team, investigator or the research staff working in consultation with the treatment team. The recruitment process presents no more than minimal risk to the privacy of the patients who are screened and minimal PHI will be used as part of a screening process. For these reasons, we seek a (partial) limited waiver of authorization for the purposes of 1) reviewing medical records to identify potential research subjects and obtain information relevant to the enrollment process; 2) conversing with patients regarding possible enrollment; 3) handling of PHI contained within those records and provided by the potential subjects.

6.3 Consent Process

Patients who meet the inclusion and exclusion criteria will be considered for the study and will be asked to sign an informed consent form.

In order to provide ample opportunity for the patient to consider participation, a copy of the consent form will be provided to all patients that verbally express interest to participate in the study. All study discussions will take place in a private exam room.

Patients will be recruited from physician referrals (internal/external physicians will only share availability of trial, same information as that already shared with the public on clinicaltrials.gov, to their patients and provide USF urology clinic or research member's contact information for further evaluation – all study recruitment will still occur at the USF urology clinic) and within our urology practice by the PI and sub-investigators. Recruitment may occur in the clinic at USF. After identifying a patient who meets minimum eligibility criteria and before collecting any study data, the study will be explained in detail to the participant including: (1) that the study represents a research effort, (2) that participation is voluntary, and there is no penalty for withdrawal, (3) any anticipated costs to the patient for participation, (4) potential risks and benefits for participation, (5) the procedures to ensure privacy of their medical information, and (6) contact information for addressing additional concerns. Patients will be informed of the purpose of the study. Only with the full and complete understanding of the study, and signed informed consent, will the evaluation of the potential participant continue. The subject will be given sufficient time to read the consent and ask any questions. Once the informed consent is signed, the subject will be given a copy of the document.

6.4 Duration of Study Participation

Study participation will require up to 2 years involvement.

6.5 Study Visits

This is a prospective, single-center, open-label study. Patients eligible for the study will undergo informed consent. Once consented, patients will be enrolled and treated with an approved open-label treatment – XIAFLEX® injection.

6.5.1 Baseline/Screening

The following procedures will be performed at the Baseline/Screening visit:

- Screen inclusion/exclusion criteria
- Obtain informed consent
- Record demographics and medical and surgical history
- Evaluate and record concomitant medications
- Administer American Urological Association (AUA) questionnaire
- Perform physical exam (as occur per standard of care)
- Perform retrograde urethrogram (RUG), voiding cystourethrogram (VCUG), post-void residual (PVR), uroflow, and cystoscopy to evaluate and document the anatomy and length and extent of spongiosal fibrosis at baseline related to the urethral stricture (as occur per standard of care).
- Perform clinic urethral ultrasound to grade urethral stricture based on previously described grading system. (Figure 1)

[figure not shown]

FIGURE 6. Clinical classification of urethral strictures based on urethra sonography. I. Short stricture with minimal spongiosal tissue involvement. II. Short stricture with moderate spongiosal tissue involvement. III. Short stricture with extensive spongiosal tissue involvement. IV. Long or multiple strictures with moderate spongiosal tissue involvement. V. Long or multiple strictures with extensive spongiosal tissue involvement.

Figure 1. Urethral stricture grading scale based on urethral ultrasound

6.5.2 Treatment (Day 0)

The following procedures will be performed on day of XIAFLEX® injection treatment:

- Evaluate and record concomitant medications
- Perform study treatment
- Assess for adverse events. Patients will be kept in clinic with vitals at 60min following injection to ensure no allergic reaction. Patients will be kept on campus until they have voided twice with a PVR <250ml or no more than 20% greater than their pre-procedural PVR.

Treatment Group – XIAFLEX® injection

On day of treatment, patients will undergo instillation of local anesthesia (20 mL of 2% urethral lidocaine jelly), the patient will undergo cystoscopy, transurethral injection (via a 70 cm 4.8 Fr flexible cystoscopic needle with a 23 gauge needle tip manufactured by Laborie®, Ontario, Canada) of 0.08ml of XIAFLEX® (0.58 mg of XIAFLEX® mixed with 0.39 mL of sterile diluent) in a single location within the stricture, chased by an additional 0.25 mL of reconstituted XIAFLEX® to allow for clearance of the original 0.08 mL of reconstituted XIAFLEX® from the transurethral syringe into the urethral stricture. This is based on 0.25 mL residual fluid that remains within the lumen of the injeTAK syringe. Thus, by adding the additional 0.25 mL of XIAFLEX® as a chase, we are expecting the original total of 0.08 mL of XIAFLEX® to be injected into the area of scarring. The depth and location of the needle will be determined pre-procedurally with urethral ultrasonography with the needle in a semi-parallel manner into the

plaque as to avoid perforation into nearby structures. Injections will be performed at a single site. The remaining 0.25 mL that remains in the injection syringe will be discarded per institutional policy for biohazard disposal.

[figure not shown]
[figure not shown]

Figure 2: Illustration of transurethral injection method for CCH injection. Note: the insertion of the needle, parallel to the direction of the urethra, to decrease the likelihood of injury to structures adjacent to the urethra.

6.5.3 Post-treatment (Days 2 or 3)

The patient will be instructed to return to clinic within 2-3 days of the injection

- Perform physical exam
- Perform uroflow, post-void residual (PVR) measurements
- Administer AUA questionnaire
- Evaluate and record concomitant medications
- Assess for adverse events

6.5.4 Post-treatment (Days 14, 28, 42, 56, 70, 84 ± 3 days)

The patient will be instructed to return to clinic every 2 weeks following treatment.

The following procedures will be performed at this visit:

- Perform physical exam
- Perform uroflow, post-void residual (PVR) measurements, and evaluate and document length and extent of spongiosclerosis every 2 weeks
- Cystoscopy and urethral ultrasonography will be performed every 4 weeks
- Administer AUA questionnaire
- Evaluate and record concomitant medications and post treatment interventions, if any
- Assess for adverse events
- Test for antibodies to AUX I and AUX II at 6 weeks and neutralizing antibodies at 12 weeks.

6.5.5 Follow-up (6, 9, 12, 18 and 24 months (\pm 7 days))

The patient will have follow-up evaluations in clinic at 6, 9, 12, 18, and 24 (\pm 7 days) months following the first treatment visit.

The following procedures will be performed at these visits:

- Perform physical exam
- Perform cystoscopy, urethral ultrasound, uroflow, PVR measurements, and evaluate length and extent of spongiosclerosis.
- Administer AUA questionnaire
- Evaluate and record concomitant medications and post treatment interventions, if any
- Assess for adverse events

6.5.6 Unscheduled Visits

If there is any medical or safety concern, the patient will be brought in earlier for re-evaluation in clinic.

The following procedures will be performed at these visits:

- Perform physical exam
- Perform cystoscopy, urethral ultrasound, uroflow, PVR measurements, and evaluate length and extent of spongiosclerosis, if applicable
- Evaluate and record concomitant medications and post treatment interventions, if any
- Assess for adverse events

6.5.7 Early Termination

Early Discontinuation

Reasons for discontinuation of treatment may include, but are not limited to, the following:

- Patient withdrawal of consent
- Any medical condition that the Investigator determines may jeopardize the patient's safety if he continues in the study
- Investigator determines it is in the best interest of the patient
- Patient noncompliance, such as missing scheduled visits, non-adherence with concomitant medications, etc.
- Lost to follow-up
- If patients have no clinical response to the intervention and have persistent clinical manifestations of their stricture disease they may elect to undergo definitive management in

the form of urethral dilation, urethrectomy, or urethral reconstruction. They will still be followed per above protocol and included in all statistical analysis.

After study treatment is discontinued, patient will be asked to remain in the study whenever possible and complete all study visits according to the planned schedule of assessments (except for patients who have withdrawn consent and are lost to follow-up). The primary reason for premature discontinuation of study treatment should be documented appropriately. If a patient chooses to discontinue study treatment and withdraw from the study, then the patient will be asked to return to the clinic for the early termination (ET) visit and complete all assessments.

Patients who prematurely discontinue study treatment will not be replaced.

Early Withdrawal

All patients have the right to withdraw from study participation without prejudice at any time during the study. If a patient terminates participation in the study, the Investigator will make a reasonable effort to determine the cause of study withdrawal. If, for whatever reason, a patient withdraws from the study or the study is terminated while the patient is receiving study treatment, an early termination (ET) visit will be performed.

Patients who prematurely withdraw from the study will not be replaced.

The following procedures will be performed at the ET visit if allowed by patient:

- Perform physical exam
- Perform cystoscopy, urethra ultrasound, uroflow, PVR measurements, and evaluate length and extent of spongiosclerosis
- Administer AUA questionnaire
- Evaluate and record concomitant medications, medical and surgical history
- Assess for adverse events

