2.1.1 Treatment of Urethral Stricture

Minimally invasive treatment options include direct vision internal urethrotomy (DVIU) and urethral dilation; these have been shown to be effective primarily on single, small bulbar strictures (<2cm), with repeated treatment being almost entirely ineffective³. Other minimally invasive treatments including urethral stents, transurethral injection with Rapamycin, botulinum toxin, or glucocorticoids have shown limited efficacy or have fallen out of favor because of increased morbidity^{4,5}. The gold standard for treatment of anterior urethral strictures involves excision of the stricture with primary anastomosis of the urethra or urethroplasty. Both surgical options, however, require extensive anesthesia and are often poor options for elderly patients, patients with significant comorbidities, or patient who simply do not wish to undergo such extensive surgery.

2.2 *Clostridium Histolyticum Collagenase*

Clostridium histolyticum collagenase (CHC) is an injectable pharmacologic agent that works by hydrolyzing collagen under physiologic environments, with in vitro studies showing CHC to be specifically selective for collagen type I and III, the predominant types found in Peyronie's plaque's and Dupuytren's contractures. Additionally, CHC spares collagen type IV, which is present within connective tissue of surrounding arteries, large veins, and nerves, limiting surrounding nerve or vessel damage⁶. CHC, marketed as XIAFLEX®, has been FDA approved for treatment of Dupuytren's disease, as well as Peyronie's disease. Large double blind studies have shown a statistically significant improvement in penile deformity following CHC injections⁷. Additionally, studies have shown significant improvement in curvature in patients who performed penile modeling with CHC.

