3.0 Study Objectives

We hypothesize that XIAFLEX® (Endo Pharmaceuticals, Dublin, Ireland) injection is an effective treatment for urethral strictures.

Primary Objectives

The primary objective is to assess the safety of clostridium histolyticum collagenase (XIAFLEX®) in treating urethral strictures.

Safety variable:

- The primary safety variable will be complication rates following treatment (XIAFLEX®)
Complications – specifically focus on pain, fever, genital lesions, or postoperative adverse events related to treatment (XIAFLEX®)

Secondary Objectives

The secondary objectives are to assess the efficacy of XIAFLEX® treatment in improving obstructive voiding dysfunction, safety of XIAFLEX® administration into urethral strictures via a transurethral approach and the quality of life following XIAFLEX® treatment.

Secondary efficacy variables:

- The primary efficacy variable will be the percentage of subjects needing further intervention for treatment of urethral stricture during the 2 years follow-up

- Further intervention – defined as any medical or surgical intervention for treatment of urethral stricture.
- Urethral stricture recurrence during the 2 years follow-up
- Elapsed time to urethral stricture recurrence during the 2 years follow-up
- Elapsed time to additional intervention for urethral stricture treatment during the 2 years follow-up
- Improvement of obstructive voiding dysfunction – defined as change in uroflow and post-void residual measurements at baseline and 6-week post treatment and follow-up visits
- Quality of Life – change in AUA scores at baseline and 6-week post treatment and follow-up visits

Secondary safety variables:

- Spongiosclerosis - incidence of formation of spongiosclerosis or change in length and extent of spongiosclerosis between the baseline and follow-up visits
- Normal urethra proximal to injected tissue – incidence of change in normal urethra structure proximal to injected tissue between baseline and follow-up visits

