6.6 Sample Size Justification

Sample size selection was based on the feasibility of completing a small number of subjects in a pilot study for safety assessments. A total of 5 patients will be enrolled in this study.

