6.7 Statistical Analysis Plan

Data analysis will be conducted using de-identified data in SPSS or SAS statistical software.

Study Population Analysis

The distributions of the following characteristics will be tabulated and presented with descriptive statistics (i.e. mean, standard deviation, median, minimum, maximum, and patient count for continuous variables, and counts with percentages for categorical variables):

- Demographics
- Medical and surgical history
- Final study exit classification (completed, discontinued, withdrew)

Primary Safety Endpoint

The primary safety variable will be complication rates following treatment (XIAFLEX®). Complications – specifically focus on pain, fever, genital lesions, or postoperative AEs related to treatment (XIAFLEX®)

Secondary Efficacy Endpoints

The secondary endpoints will be evaluated with the following tests:

- The percentage of subjects needing further intervention for treatment of urethral stricture during the 2 years follow-up. Further intervention – defined as any medical or surgical intervention for treatment of urethral stricture.
- Incidence of urethral stricture recurrence within 2 years following initial treatment will be calculated and presented with descriptive statistics
- Elapsed time to urethral stricture recurrence and elapsed time to additional intervention for urethral stricture treatment within 2 years following initial treatment will be calculated and presented with descriptive statistics
- Efficacy of XIAFLEX® treatment in improving obstructive voiding dysfunction will be analyzed using paired t-test for the difference in uroflow and post-void residual measurements before and after study treatment (collected at baseline, 6-week post treatment and follow-up visits)
- Quality of life will be analyzed using paired t-test for the difference in AUA scores before and after study initial treatment (collected at baseline, 6-week post treatment and follow-up visits)

Secondary Safety Endpoints

The results of the following safety endpoints will be calculated and presented with descriptive statistics for all patients receiving study treatment.

- Complication rates following treatment – specifically pain, fever, genital lesions, or postoperative complaints secondary to treatment
- Incidence of formation of spongiosclerosis or change in length and extent of spongiosclerosis
- Incidence of change in normal urethra structure proximal to injected tissue

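### Both structural safety endpoints take in findings made after stricture surgery, so their incidence can mix the effect of the operation with that of XIAFLEX

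*Combined protocol and SAP*

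**What the plan says.** Section 3.0 names two structural secondary safety variables. The first is spongiofibrosis (the text prints several spellings): "incidence of formation of spongiosclerosis or change in length and extent of spongiosclerosis between the baseline and follow-up visits". The second concerns the urethra upstream of the injection: "incidence of change in normal urethra structure proximal to injected tissue between baseline and follow-up visits". Section 6.7 lists both for descriptive summary in everyone who received study treatment, the second as "Incidence of change in normal urethra structure proximal to injected tissue".

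Section 6.5.7 allows a man with no clinical response and persisting stricture disease to choose dilation, urethrectomy or reconstruction. It then states: "They will still be followed per above protocol and included in all statistical analysis". No endpoint is exempted. Section 6.5.5 sets the same examinations at months 6, 9, 12, 18 and 24, with no exception after a repair: "Perform cystoscopy, urethral ultrasound, uroflow, PVR measurements, and evaluate length and extent of spongiosclerosis".

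The background in Section 2.1.1 describes the gold standard for anterior strictures as "excision of the stricture with primary anastomosis of the urethra or urethroplasty". On size, Section 6.6 says: "A total of 5 patients will be enrolled in this study". There is one arm and no control.

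**The concern.** Spongiofibrosis and the proximal urethra are imaged to learn what the injected enzyme does to tissue. A later operation on the same stricture also changes that tissue. It can leave new scar, or it can take away tissue that had changed after the injection. The rule in Section 6.5.7 carries the post-operative images into both endpoints, and Section 6.7 has no step that separates them.

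The primary complication endpoint is limited to events related to XIAFLEX, and Section 9.1 has a relatedness scale for adverse events. The two structural endpoints have no such filter. Section 3.0 also gives no direction for the change in length and extent, so fibrosis shortened by excision could be counted as a safety event.

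At stake is the structural safety result of a 5-man trial whose primary objective is safety. It could show a signal that surgery caused, or lose one that the drug caused.

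**Working it through.** **No stated figure to reproduce.** The sample size has no statistical inputs: "Sample size selection was based on the feasibility of completing a small number of subjects in a pilot study for safety assessments". The check therefore sets the rules side by side and sizes the consequence under stated assumptions.

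**Step 1: the rules together.**
- Who is counted: all treated men (6.7), expressly including repaired men (6.5.7).
- What is compared: baseline with the follow-up visits (3.0). The plan does not say which follow-up visit decides the score.
- What is excluded: nothing. No text stops, splits or attributes the score at a procedure.

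**Step 2: what each procedure does to the comparison.**
- Dilation or incision: the score can still be obtained. Section 4.1 admits men who have already failed measures such as internal urethrotomy (DVIU) or balloon dilation, and Section 6.5.1 documents their spongiofibrosis at baseline. A change first seen after a new procedure cannot, however, be attributed to the drug.
- Excision or reconstruction of the injected segment: attribution is lost, and the baseline comparison may also lose its reference tissue. Section 4.2 excludes prior urethroplasty, so no man starts from that state.

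**Step 3: false signal.** With n = 5, each repaired man scored as changed moves the incidence by 1/5 = 20 points. The intervals below are exact (Clopper-Pearson) 95% intervals, added here because the plan specifies none. The lower limit is the 2.5% quantile of Beta(x, n − x + 1), and the upper is the 97.5% quantile of Beta(x + 1, n − x). For x = 0 the upper limit is 1 − 0.025^(1/n).

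| Men scored as changed | Incidence | Exact 95% CI |
|---|---|---|
| 0 of 5 | 0% | 0% to 52.2% |
| 1 of 5 | 20% | 0.5% to 71.6% |
| 2 of 5 | 40% | 5.3% to 85.3% |

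If the drug changes nothing and 1 or 2 repaired men are scored as changed, the report reads as row 2 or 3 instead of row 1.

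**Step 4: how likely a repair is.** The plan gives no rate q, so a range is assumed. The chance of at least one repaired man is 1 − (1 − q)^5:
- q = 10%: 1 − 0.9^5 = 41%
- q = 20%: 1 − 0.8^5 = 67%
- q = 30%: 1 − 0.7^5 = 83%
- q = 50%: 1 − 0.5^5 = 97%

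**Step 5: hidden signal.** Suppose a true drug-related incidence p, an independent repaired share q, repair that removes the changed tissue, and only post-repair scores counting. The expected reported incidence is p(1 − q). With p = q = 40% it is 0.4 × 0.6 = 24%.

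**Step 6: how much imaging is affected.** Ultrasound every 4 weeks to Day 84 gives Days 28, 56 and 84, which is 3. Months 6, 9, 12, 18 and 24 add 5, for a total of 8. A man repaired soon after Day 84 has 5 of 8 after surgery.

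**Step 7: the alternatives.** Take one repaired man with no change before repair, and no drug effect in anyone. Using his pre-procedure examinations gives 0/5 (0% to 52.2%). Dropping him gives 0/4, with upper limit 1 − 0.025^(1/4) = 60.2%. Cutting his series at the procedure keeps the denominator. Removing him does not.

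**The case against.** The case on the other side has real force.

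- **Scoring after a procedure.** A reader might infer that the endpoints cannot be scored once the segment has been cut. The documents do not support that, because spongiofibrosis is graded at baseline in men who already failed DVIU or dilation. Nor do they show that the proximal urethra is always operated on. The stricture is single, bulbar and at most 2 cm, the injection site is recorded (5.4), and the urethra above it may stay assessable, depending on the repair. Section 6.5.7 does not name excision with anastomosis. That comes from the background.
- **Separating the two effects.** A reader might infer that, without a control arm, nothing in the data can do this. In fact interventions are recorded at visits (6.5.4 to 6.5.6), time to additional intervention is a planned endpoint, and imaging is serial. Findings before and after a procedure can be told apart. What is missing is the rule to do so.
- **Keeping repaired men.** Following every treated man is sound. Section 8.0 lists new scar and later reconstruction as risks, and Section 9.4 stops the study if treatment harms a later intervention. Post-repair anatomy therefore matters for safety and should not disappear.
- **Size.** No repair rate is given. The 20% and 40% figures need each repaired man to be scored as changed and no drug effect, and their intervals overlap widely with that for 0 of 5. The endpoints are secondary and descriptive.

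All four points limit the claim. None supplies a rule for post-procedure scores, and the rule that does exist puts them in.

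**Conclusion.** The concern holds in a conditional form. Followed as written, Section 6.5.7 with Sections 3.0 and 6.7 allows post-procedure anatomy to enter both structural safety incidences with no limit to drug-related change. The mixing occurs if a man is repaired and either a change is first scored afterwards or the repair removes tissue that had changed. It is tempting to say that surgical effects will be reported as XIAFLEX effects. The documents do not go that far: no repair may occur, a change seen before repair would be counted correctly, and the deciding visit is not specified.

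The effect is 20 percentage points per affected man, upward if surgical change is counted and downward if drug-related change is erased. The number of affected men is an assumption, since the plan gives no repair rate. At least one repair is more likely than not at an assumed rate of 20% or more. The defect is confined to these two endpoints.

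**What to change.** **Section 6.7 (and the matching text in the Section 1.0 synopsis).** Base the main incidence of both structural endpoints on examinations up to the last one before the first surgical or instrumental procedure on the urethra for stricture. Keep all 5 treated men in the denominator, and keep any event already seen by then. Do not use the plan's definition of further intervention as the cut-off: it includes medical treatment, which would end scoring with the segment untouched. State how many men had no post-injection structural examination before their procedure.

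Report post-procedure findings, and the incidence over all visits, separately by type and date of procedure, so that a late drug effect stays visible.

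**Section 6.5.7.** Keep the sentence on follow-up and inclusion, and add: *with the two structural safety endpoints summarised before and after the procedure as stated in 6.7*. Repaired men then stay in the intervention, recurrence, voiding, AUA and adverse-event analyses.

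**Cost.** Wording only, with no new visit, procedure or data item. The main incidence has shorter structural follow-up in repaired men. A change arising between the last examination and the procedure, a gap of about 6 months between the month 12 and 18 visits, would appear only in the separate report.
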